9.3. Microbiology

Microbiology results will be presented by descriptive statistics for the ITT Analysis Set.

Number and percentage of participants with any microbial detection in quantitative measures will be summarized by scheduled visit. Descriptive statistics will be provided for change from baseline in the number of colony-forming units.

For microbials in qualitative measures, a shift summary for the categories will be provided from Baseline to Day 28/Last Visit.

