## **8. STUDY ASSESSMENTS AND PROCEDURES**

Study procedures and timing are summarized in the SoA. Protocol waivers or exemptions are not allowed.

Immediate safety concerns should be discussed with the Sponsor immediately upon occurrence or awareness to determine if the participant should continue or discontinue study drug.

Adherence to the study design requirements, including those specified in the SoA, is essential and required for study conduct.

All screening evaluations must be completed and reviewed to confirm that potential participants meet all eligibility criteria. The Investigator will maintain a screening log to record details of all participants screened and to confirm eligibility or record reasons for screening failure, as applicable.

The maximum amount of blood collected from each participant over the duration of the study, including any extra assessments that may be required, will not exceed 6 mL.

Sputum sample collection will be attempted on all participants able to provide a sample either spontaneously, with chest physiotherapy, or by induction. Although sputum collection is an important exploratory PD analysis, in light of the potential challenges obtaining an adequate sample due to the concomitant administration of CFTR modulators, sputum collection will be attempted on all participants per local practice, however, sputum collection will not be required for participants who cannot provide sputum. Sputum sample collection will be prioritized for PD analyses, and if there is sample remaining, microbiology will be assessed.

The study centers may use their own sputum induction protocols or the sputum induction guidelines provided in Appendix Section [10.5](#).

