ICE	
 • Early discontinuation from randomized IP for any reason
Strategy	The While-On-Treatment strategy will be applied.

FEV₁ = forced expiratory volume in 1 second, ppFEV₁ = percent predicted forced expiratory volume in 1 second, FVC = forced vital capacity, FEF_(25-75%) = forced expiratory flow between 25% and 75% of forced vital capacity.

Efficacy Objective(s)	
To evaluate the effect of brensocatib compared with placebo on quality of life (QoL) as measured by cystic fibrosis questionnaire (revised version) (CFQ-R) ¹ through the 4-week treatment period	
Population	Participants with CF defined by the inclusion and exclusion criteria of the CSP
Treatment Regimen	1 tablet QD of brensocatib or placebo (randomized treatment)
Endpoints	Change from Baseline to Day 14 and Day 28 for the CFQ-R Respiratory Domain score
Population Level Summary	Treatment means or difference in means if data allow estimation based on a statistical model
ICE	
 • Early discontinuation from the randomized IP for any reason
Strategy	The While-On-Treatment strategy (including up to Day 35 follow-up period) will be applied.

CFQ-R = Cystic Fibrosis Questionnaire-Revised.

Microbiology Objective(s)	
To evaluate the effect of brensocatib on sputum microbiology	
Population	Participants with CF defined by the inclusion and exclusion criteria of the CSP
Treatment Regimen	1 tablet QD of brensocatib or placebo (randomized treatment)
Endpoints	Change from Baseline to Day 28 in number of colony-forming units for microbial species
Population Level Summary	Treatment means and change from baseline
ICE	
 • Early discontinuation from randomized IP for any reason
Strategy	The While-On-Treatment strategy will be applied.

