4. STUDY DESIGN

4.1. Summary of Study Design

This is a Phase 2a, single-blind, randomized, placebo-controlled, parallel-group, multiple-dose study to assess the PK, PD, and safety of brensocatib 10, 25, and 40 mg QD in participants with CF. Following review of PK and safety data by a SRC, and provided that the SRC deems it appropriate to administer the next dose, a cohort of participants will receive brensocatib 65 mg QD on the same schedule as the previous cohorts. A tablet formulation of brensocatib 65 mg is not yet available; therefore, participants assigned to the 65 mg dose cohort will receive 1 tablet of brensocatib 25 mg and 1 tablet of brensocatib 40 mg.

Overall, the study will enroll approximately 25 to 34 participants. The first three brensocatib arms (10 mg, 25 mg, and 40 mg QD) will enroll approximately 7 participants each, and the placebo arm will enroll approximately 4 participants. For the active treatment arms, there will be 2 strata: 5 participants who have previously received and will continue to receive CFTR modulators as concomitant medication (CFTR modulator stratum), and approximately 2 participants who have either never previously received CFTR modulators or have not been administered CFTR modulators within 30 days prior to Screening (Visit 1) and will not receive CFTR modulators during the study (non-modulator stratum). For the placebo arm, approximately 3 participants will be randomized into the CFTR modulator stratum and 1 participant in the non-modulator stratum.

Each dose group will enroll participants in a 5:1 ratio (active : placebo) for the CFTR modulator stratum. For the non-modulator stratum, approximately 6 participants will be randomized to receive active treatment (10 mg, 25 mg, or 40 mg brensocatib) and approximately 1 participant to placebo.

If there are no safety issues observed in the first 3 dose cohorts, a 65 mg dose cohort will be similarly randomized: 7 participants (5 participants CFTR modulator and 2 participants non-modulator stratum) in active treatment and 2 participants in placebo (1 participant each in the CFTR modulator and non-modulator strata), increasing the sample size from approximately 25 to 34 participants.

The overview below illustrates the prospective number of participants based on approximately 25 participants in the first 3 cohorts (10 mg, 25 mg, and 40 mg) and approximately 9 participants in the fourth cohort (65 mg).

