7. GENERAL STATISTICAL CONSIDERATIONS

7.1. General

Tables and figures will be provided by treatment group/dose level (10 mg, 25 mg, 40 mg, and 65 mg [if conducted] QD brensocatic, pooled placebo except for PK output). If sample sizes permit, summaries will be further stratified by CFTR modulator and non-modulator.

Treatment arm/dose levels will be presented in this stratified analysis if the number of observations is ≥ 2 . If the assignment to a stratum differs between the randomization file and the eCRF, the randomization file will prevail. In the listings, CFTR modulator use will be indicated by + for participants on CFTR modulator and by - for the non-modulator stratum following the Subject Identifier. For tables in the demographic and safety sections, also a Total column will be presented.

Descriptive statistics for continuous variables will be calculated at scheduled visits (nominal timepoints for PK) and will include the number of participants in the treatment group/dose level of the respective analysis set (N in column header of the table), the number of non-missing- observations (n), the number of observations below limit of quantification (BLQ) for PK and PD tests, arithmetic mean, standard deviation (SD), median, minimum, and maximum. For brensocatic plasma concentrations, the GM with 95% CI and gCV%, for PK parameters (except for t_{\max} and t_{last}), and PD tests, the GM and gCV% will be reported in addition. The GM will be derived by calculating the arithmetic mean of the natural log-transformed observations and then back-transforming the mean by exponentiation. The gCV% will be calculated as: $100 \times \sqrt{\exp[\text{variance of the log-transformed values}] - 1}$. GM and gCV% will only be calculated for quantifiable values above 0. For t_{\max} and t_{last} , only n, median, minimum, and maximum will be presented. For PK parameters, no descriptive statistics will be calculated when fewer than three individual PK parameter values are available. Summaries of continuous variables other than plasma concentrations that have some values recorded using approximate values (e.g., $<$ or $>$) will use the numeric part of the value in calculations. Rules for plasma concentrations BLQ or missing are given in [Section 11](#).

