Categorical variables will be summarized by counts and by percentage of participants in the corresponding categories. The number of participants in the treatment group/dose level of the respective analysis set (N in column header of the table) and the number and percentage of non-missing observations in each category will be provided. A category including missing assessments may be added if appropriate. Footnotes will specify the base for the percentages.

Data from unscheduled visits will not be used in summaries, except for the derivation of baseline.

Listings corresponding to all summaries will be provided. Listings will also show data from unscheduled visits. Listings will be presented by treatment group/dose level, Subject Identifier, and date or visit. Listings will present the data as collected in the eCRF along with variables derived from the eCRF data.

The baseline value for safety data will be the most recent non-missing value prior to the first dose of IP.

The baseline value for efficacy data will be the most recent non-missing value prior to randomization. Note that for PFT, the most recent best effort prior to randomization will be selected.

Change from baseline at visit (i) = observed value at visit (i) – baseline value.

Percent change from baseline at visit (i) =

$$100 * [(observed\ value\ at\ visit\ (i) - baseline\ value) / baseline\ value].$$

Percent inhibition from baseline at visit (i) = $100 * [1 - \text{fold change from baseline at visit (i)}]$,
where fold change from baseline at visit (i) = observed value at visit (i) / baseline value.

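### Sputum microbiology is summarised as mean change in raw colony-forming units; if counts are strongly skewed, one participant can dominate an arm of seven or fewer and the sign of the mean can mislead

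*SAP*

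**What the plan says.** The microbiology endpoint in SAP 3.3 is "Change from Baseline to Day 28 in number of colony-forming units for microbial species", and its population-level summary is "Treatment means and change from baseline". SAP 9.3 gives the analysis: "Descriptive statistics will be provided for change from baseline in the number of colony-forming units". It adds the number and percentage of participants with any microbial detection and a shift table for qualitative results.

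SAP 7.1 supplies the general rules:
- Change is the observed value minus the baseline value, on the scale recorded.
- Continuous variables receive "arithmetic mean, standard deviation (SD), median, minimum, and maximum".
- Geometric statistics go to plasma concentrations and to PK parameters "and PD tests, the GM and gCV% will be reported in addition". Microbiology is not in that list.
- Every summary has a listing.

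Protocol 9.4.4 says only that species and colony-forming units will be listed and summarised by dose level and placebo.

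On numbers, SAP 4.1 says the first three active arms "will enroll approximately 7 participants each, and the placebo arm will enroll approximately 4 participants". Placebo rises to about 6 if the 65 mg cohort is run (SAP Table 1). Protocol section 8 adds: "Sputum sample collection will be prioritized for PD analyses, and if there is sample remaining, microbiology will be assessed". The number with microbiology data, by species, may therefore be below the arm size.

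**The concern.** A mean of raw count differences weights each participant by the size of his or her count. Where counts differ by powers of ten, a tenfold change from 10^7 outweighs a tenfold change from 10^5 a hundred to one, although both are the same proportional change. In an arm of 7 or fewer the mean can then reflect one person.

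Opposite movements within an arm are plausible here, because Protocol 4.1.2 lets participants enter at the start of either the on-treatment or the off-treatment part of an antibiotic cycle. Mixed movements are where the raw mean misleads most. At stake is whether the reported mean change in bacterial load points the same way as the change in most participants.

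**Working it through.** **No figure to reproduce.** The documents give no mean, SD, range or detection limit for CFU. Every CFU value below is an assumption.

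**Step 1: a worked arm of 7 (assumed values).**

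| Participant | Baseline | Day 28 | Raw change | log10 change |
|---|---|---|---|---|
| 1, 2 | 10^5 | 10^4 | -90,000 each | -1 |
| 3, 4, 5 | 10^6 | 10^5 | -900,000 each | -1 |
| 6 | 10^7 | 10^6 | -9,000,000 | -1 |
| 7 | 10^7 | 10^8 | +90,000,000 | +1 |

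- Sum of raw changes: -180,000 - 2,700,000 - 9,000,000 + 90,000,000 = 78,120,000. Raw mean: 78,120,000/7 = +11,160,000, a rise.
- Median raw change: -900,000, a fall.
- Raw mean without participant 7: -11,880,000/6 = -1,980,000.
- Mean log10 change: (6 × (-1) + 1)/7 = -0.71. The geometric mean ratio, Day 28 to Baseline, is 10^-0.71 = 0.19, a fall.

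Six of seven participants fall tenfold and the raw mean shows a rise.

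**Step 2: how often this happens.** Simulated arms of n=7, with log10 CFU normal, baseline mean 6.5 and total baseline SD 1.5. Three noise models were used:
- A: noise of SD 0.8 log10 added at Day 28 only.
- B: noise of SD 0.8 log10 at each visit.
- C: noise at both visits, scaled so that the change has SD 0.8 log10.

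Percentage of arms in which each summary shows a rise:

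| True change | Model | Raw mean | log10 mean | Planned median |
|---|---|---|---|---|
| -0.5 log10 | A | 33 | 5 | 9 |
| -0.5 log10 | B | 26 | 12 | 17 |
| -0.5 log10 | C | 20 | 5 | 9 |
| -1 log10 | A | 11 | <0.1 | 0.3 |
| -1 log10 | B | 10 | 1 | 3 |
| -1 log10 | C | 5 | <0.1 | 0.3 |

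The largest single change supplies a median of about 76-80% of the summed absolute change in every model.

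**Step 3: sensitivity to the assumed spread.** Here the centre was 10^6, the mean change -0.5 or -1 log10, the SD of change 0.5 or 1 log10, and the change was added to the baseline value, as in model A.

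| Baseline SD (log10) | n | Median share of largest change | Raw mean and median of opposite sign |
|---|---|---|---|
| 1 to 2 | 7 | 62-87% | 1-39% of arms |
| 1 to 2 | 4 | 73-93% | 1-24% of arms |
| 0.25 to 0.5 | 7 | 28-53% | 0.3-50% of arms |

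Opposite signs are rare, about 0.3-2%, when the fall is uniform (-1 log10, SD of change 0.5). They are common, about 14-50%, when the SD of change is 1 log10.

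**The case against.** The strongest reply is that the plan does not rest on the mean alone. SAP 7.1 puts the median, minimum and maximum beside it and lists every count. A participant's raw change and log10 change always have the same sign, so with 7 observations the median raw change and the median log10 change also agree in sign. The table would therefore already show the typical direction. This stands, and it lowers the stakes. It does not remove the point: the estimand names means, and a median of raw differences is still in CFU and gives no fold change.

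A reader might also infer more than the documents support:
- *That the raw mean leans towards a rise even with no drug effect.* This appears only when noise is placed on Day 28 alone, which builds an increase in expected CFU into the no-effect case. With noise at both visits the raw mean is positive in 50% of arms, as on the log scale.
- *That the assessment of infection risk or the 65 mg decision depends on this mean.* Infections are followed as adverse events of special interest (Protocol 8.2.7.3, SAP 10.2.1). The data listed for the Safety Review Committee (Protocol 4.1.5, SAP 5.1) are PK, PD, vital signs, laboratory tests, ECGs and adverse events. Microbiology is not named.
- *That the documents show CFU to be strongly skewed.* They give no distribution. The size of the problem depends on the assumed spread.

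Finally, a log10 summary needs a value for no growth. With few samples per species that value can itself move the log mean. This is a fair cost and belongs in the fix.

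**Conclusion.** The point holds as a modest improvement to an exploratory, descriptive endpoint. The plan averages raw CFU differences, reserves geometric statistics for other data, and applies this to arms of about 7 or fewer. If counts are strongly skewed, one participant can dominate the mean and its sign can differ from the typical change.

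At an assumed baseline SD of 1.5 log10, a raw mean shows a rise despite a true 0.5-log fall about 2 to 7 times as often as a log10 mean does (26/12 = 2.2 in model B, 33/5 = 6.6 in model A). The planned median lies between the two. The excess shrinks to near nothing when participants all move alike. No hypothesis test, confidence interval or between-arm comparison is planned for CFU, so no primary, secondary or stated committee decision is affected.

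**What to change.** In SAP 9.3, and in the endpoint and summary rows of the microbiology estimand in SAP 3.3:
- Define the endpoint as change in log10 CFU by species.
- Report mean, SD and median on the log10 scale, with the mean back-transformed as a Day 28 to Baseline geometric mean ratio.
- State in advance the value used for no growth, tied to the assay detection limit. SAP 7.1 uses the numeric part of values recorded with a < or > sign but does not say how no growth enters. The documents do not give the limit, so the laboratory must supply it.
- Report the number of no-growth results at each visit beside the mean and median, so that a reader can see how far the substituted value drives the log mean.
- Keep raw counts in the listings.

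The cost is SAP wording and one agreed convention before database lock. No new data, visits or samples are needed.

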10. SAFETY

For the general layout of the tables see [Section 7.1](#).

Analyses will be based on the Safety Analysis Set, unless otherwise stated.

Unless otherwise stated all summaries will have corresponding listings.

10.1. Study Drug Exposure and Compliance

10.1.1. Treatment and Study Duration

Duration of study, actual and planned treatment are Safety components and will be analyzed for the Safety and PK Analysis Sets.

Study duration will be calculated as number of days between randomization and EoS visit:

$$\text{study duration (days)} = \text{date of EoS visit} - \text{date of randomization} + 1$$

Actual treatment duration will be calculated as

$$\text{actual treatment duration (days)} = \text{date of last dose} - \text{date of first dose} + 1$$

This definition does not account for protocol-allowed dose interruptions for safety reasons.

IP exposure duration will be calculated as:

$$\text{exposure duration (days)} = \text{actual treatment duration} - \text{number of missed doses if reason was AE.}$$

Descriptive statistics will be provided for duration of

- study,
- treatment and
- exposure.

Number and percentage of participants will be presented for categories of treatment duration

- ≤ 7 days,
- >7 to ≤ 14 days,
- >14 to ≤ 21 days,
- >21 to ≤ 28 days,
- >28 days.

The last category is inserted to confirm compliance with the planned treatment duration.

10.1.2. Dose Interruptions

Dose interruptions will be recorded in the eCRF as number of missed doses, reason, and start and end date of dose interruption. The number and percentage of participants with missed IP doses by reason and descriptive statistics for the number of missed doses by reason will be presented. Summary tables will be given for the PK and the Safety Analysis Sets.

10.1.3. Compliance

Compliance summary tables will be provided for the PK Analysis Set. The listings will be provided for the Safety Analysis Set. The actual treatment will be compared with the planned treatment.

Participants will be required to bring all their used and unused IP supplies to in-clinic study visits during the treatment period or, if the visit is being conducted virtually, have all used and unused IP supplies available to be accounted for.

The number of expected doses will be calculated based on the planned treatment duration (since the therapy is prescribed QD) and the number of missed doses due to AE (see [Section 10.1.1](#)). At days of interruption of IP due to safety reasons (reason for interruption = ‘Adverse Event’) no doses are expected. Drug is dispensed at the Day 1 and Day 14 visit and returned drug is counted at the Day 14 and Day 28 visit, respectively. To assess compliance, the planned treatment duration will be calculated for these periods based on the visit dates as:

Day 1 to Day 13:

Planned treatment period (days) = Day 14 visit date – Day 1 visit date.

Day 14 to Day 28:

Planned treatment period (days) = Day 28 visit date – Day 14 visit date + 1.

Day 1 to Day 28:

Planned treatment period (days) = Day 28 visit date – Day 1 visit date + 1.

The planned treatment duration from Day 1 to Day 28 may vary between 24 and 32 days due to a time window of ± 2 days allowed at the Day 14 and Day 28 visit. If a participant has a planned treatment duration of less than 24 or more than 32 days, the planned treatment duration will be set to 24 or 32 days, respectively, for the calculation of compliance.

Expected doses = planned treatment period - number of missed doses if reason was AE.

Compliance (%) = $100 \times (\text{number of randomized doses} / \text{number of expected doses})$.

If the actual treatment differs from the randomized treatment, tablets in the actual treatment will not be counted for the number of randomized doses.

Compliance to IP will be categorized (<80%, 80-120%, >120%) and summarized by number and percentage of participants in the categories and descriptive statistics for the continuous compliance value.

10.2. Adverse Events

The second primary endpoint is the incidence of TEAEs. The strategies as outlined in [Section 3.1](#) and [Section 7.2](#) will be applied for ICEs.

The AE verbatim descriptions (Investigator terms from the eCRF) will be coded by standardized medical terminology using MedDRA. AEs will be coded to primary SOC and PT using the most recent MedDRA version.

A TEAE is defined as any AE that occurs on or after the first dose of IP and within 28 days after the last dose of IP. AEs that occur between the time the participant had signed the Informed Consent Form for the study and before the participant receives the first dose of IP on Study Day 1 will be summarized as medical history and not as an AE unless the event meets the definition of a serious adverse event (SAE).

Where AE start dates are missing or partially missing, AEs will be assumed to be treatment-emergent, unless the partial start date or the AE end date gives clear evidence that the AE started before the first administration of IP.

Table 4: TEAE Assignment in Case of Missing AE Start Date Elements

Missing elements of AE start	Rule (IP start = first dose of IP)	Classification
Regardless of any missing information for AE start: AE end date < IP start date		non-TEAE
Otherwise (i.e., if AE end date \geq IP start date)		
- day/month/year	all AEs	TEAE
- day and month	AE start year \geq IP start year	TEAE
	AE start year < IP start year	non-TEAE
- day	AE start month/year \geq IP start month/year	TEAE
	AE start month/year < IP start month/year	non-TEAE

Duration of AEs will be calculated in days as:

$$\text{AE end date} - \text{AE start date} + 1.$$

If the start or the end date of the AE is not complete, the duration cannot be calculated and will be missing.

Summaries that are displayed by SOC and PT or by PT and will be ordered by descending order of total number of participants of SOC and PT within each SOC or by descending order of total number of participants of PT. SOC and PTs with the same number of participants will further be ordered by number of events. In the case of the same number of events, SOC and PTs will be ordered alphabetically.

Summary tables will present number and percentage of participants with TEAEs and number of events.

The following tables will be presented:

- Overall summary of TEAEs, specifically participants with at least one:
 - TEAE,
 - TEAE related to IP,
 - serious TEAE,
 - serious TEAE related to IP,
 - TEAE resulting in death,
 - TEAE of special interest (TEAESI),
 - TEAE leading to withdrawal from the study/IP, and
 - TEAE related to COVID-19.
- Participant incidence of TEAEs and number of TEAEs by MedDRA SOC and PT (for ordering see specification above):
 - TEAEs,

- TEAEs related to IP,
 - TEAEs by severity,
 - TEAEs leading to study/IP withdrawal,
 - TEAEs related to COVID-19,
 - serious TEAEs, and
 - serious TEAEs related to IP.
- Participant incidence of TEAEs and number of TEAEs by MedDRA PT (for ordering see specification above).

All AEs will be listed.

